6.1 Study Subjects

6.1.1 Disposition of Subjects

Subject disposition (e.g., number completing the study, number lost-to-follow-up) will be summarized with frequency tables. For subjects exiting the trial, the reason for termination will be presented. For the B-271 Cytosponge study, there is only one planned follow-up at 7 days (+/- 3 days) following the Cytosponge and upper endoscopy procedures.

6.1.2 Clinical Investigation Plan (CIP) Deviations

Discuss potential CIP deviations or violations and how they will be reported.

6.1.3 Analysis Sets

Subjects will be considered enrolled in the study once it has been confirmed that they meet all the inclusion and none of exclusion criteria. Unless otherwise specified, analysis of reported outcomes will include all available data for all subjects enrolled.

6.2 General Methodology

All statistical analyses were performed using SAS statistical software. Descriptive statistics were provided for all variables summarized. The statistics for continuous variables may have included mean, standard deviation, minimum, maximum and the number of observations (N). Categorical variables are described with frequencies and percentages.

6.3 Handling of Missing, Unused, and Spurious Data and Dropouts

No imputation or other adjustment techniques are planned for the missing data to be included in the analyses. All data will be included unless judged to be invalid.

6.4 Demographic and Other Baseline Characteristics

The baseline characteristics, including age at time of procedure, gender, race, ethnicity, weight, height, smoking history, alcohol assumption, and baseline histology of BE and GERD symptoms subjects, will be

Revision 2.0

Page 11 of 13

summarized. Discrete variables will be presented using frequency distributions and cross tabulations. For continuous variables, statistics will include the number of observations (N), mean, standard deviation, median, minimum, and maximum values.

6.5 Interim Analyses

In an effort to understand the sensitivity and specificity of the test, an interim analysis of the data, based on the statistical methodology outlined above, may be performed after approximately half the study subjects have primary outcomes.

6.6 Evaluation of Objectives

6.6.1 Primary Objectives

The following 2 primary objectives will be assessed:

6.6.1.1 Primary Objective 1

To assess the acceptability of a novel, minimally invasive esophageal mucosal sampling technique, the Cytosponge, in subjects undergoing surveillance of BE, and 2) in subjects with GERD symptoms undergoing screening for BE. Based on previous data, it is expected that the sponge-based sampling technique will be associated with low levels of subject distress, and will be preferred by subjects, when compared to standard sedated upper endoscopy.

Acceptability of the Cytosponge

The acceptability of the Cytosponge will be measured using impact of event scale, a visual analog scale. The scale yields two scores assessing intrusive and avoidance thoughts. Data will be compared to population norms in published literature¹. The VAS scores for pain will be calculated as well.

We will measure the central tendency and distribution of impact of event scale scores, as well as the intrusiveness and avoidance subscales. Bivariate analysis will be performed to assess predictors of low tolerance of Cytosponge surveillance, and a logistic regression model will be created to assess these factors while controlling for potential confounders.

Procedure preference and acceptability

[figure not shown]
Subjects' preferences for Cytosponge versus endoscopic surveillance, as well as willingness to undergo the procedure again, will be summarized with frequency and percentages. Univariate and multivariate logistic regression analyses for predictors of the procedure preference will be performed.

6.6.1.1.1 Primary Objective 2

To assess the adequacy of cytology samples obtained by Cytosponge after 1 sampling, and after 2 samplings if first sample inadequate. Based on previous data, it is expected that the Cytosponge will harvest adequate amounts of esophageal cells to perform pelleting, centrifugation sectioning and

Revision 2.0

Page 12 of 13

staining for TFF3, a reliable biomarker of intestinal metaplasia. For purposes of this investigation, an adequate sample will be one in which at least one columnar cell on H&E staining is present. If the initial administration of the Cytosponge demonstrates an inadequate sample, repeat Cytosponge administration will be performed at 30 days (+/- 10 days) from the initial administration.

Sample Adequacy

Sample adequacy will be treated as a binary variable. It will be presented as a proportion of subjects who fulfill this definition after up to two total administrations of the Cytosponge, as noted in the methods.

All individuals offered the Cytosponge will be included in analyses of acceptability and adequacy of sampling.

6.6.1.1.2 Secondary Objectives

6.6.1.1.3 Secondary Objective 1

To assess the operating characteristics of Cytosponge against a gold standard of upper endoscopy with biopsies for endoscopic surveillance in subjects with BE who demonstrate an adequate sample on Cytosponge assessment. It is expected that the assay will demonstrate both a sensitivity and specificity of > 90% in the detection of BE. Further, we expect higher accuracy in those with a larger burden of disease.

6.6.1.1.4 Secondary Objective 2

[figure not shown]
To assess the operating characteristics of Cytosponge against the worst ever histology documented in the subject.

6.6.1.1.5 Secondary Objective 3

To assess the operating characteristics of Cytosponge as a function of baseline histology. To date, no data are available regarding the yield of Cytosponge in Subjects with BE and more advanced disease (low-grade dysplasia and high-grade dysplasia). These subjects are at greatest risk for progression to cancer. We plan to collect pilot data on operating characteristics of the assay by degree of baseline dysplasia. It is expected that Cytosponge will perform with similar operating characteristics in this group compared to non-dysplastic BE.

For the secondary objective 1, 2 and 3, to assess the operating characteristics of Cytosponge against various gold standards, two-by-two tables will be constructed demonstrating Cytosponge and the gold standard findings (Y/N for BE). Sensitivity, specificity, positive predictive value, negative predictive value and accuracy will be calculated.

Revision 2.0

Page 13 of 13

6.6.1.1.6 Secondary Objective 4

To assess the degree of mucosal abrasion following Cytosponge administration, endoscopic abrasion score, a standardized scale, will be calculated. The distal extend of cells collected by recording the location of abrasions as well as their grade. Based on previous data, it is expected that mucosal damage due to abrasion by the Cytosponge will be minor. Further, the distal extent of the abrasion will correlate with the presence of columnar cells on the H&E slide made from Cytosponge samples in the sample.

6.6.1.1.7 Secondary Objective 5

To assess safety, the number and percentage of subjects with adverse events (AEs) related to Cytosponge administration will be summarized by MedDRA system organ class and preferred term overall, and by severity.

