4.2. Purpose

EAC is a lethal cancer with a rapidly increasing incidence. In stark contrast to recent progress in treating other solid tumors, incidence and death rates from EAC continue to rise rapidly in the U.S. There has been a 500% increase in the incidence of EAC from the 1970s to the 1990s,³ and a nearparallel increase in mortality (Figure 1), underscoring the need for more effective prevention and treatment for this lethal cancer. Esophageal adenocarcinoma is thought to develop through a series of metaplastic, then dysplastic, changes of the mucosa.⁴ GERD precipitates a

metaplastic change from the normal squamous epithelium, to Figure 1 Incidence (top curve) and a more acid-resistant columnar histology.⁵ When this columnar epithelium contains goblet cells, it is termed

associated mortality (lower) of EAC²⁵

specialized or intestinalized metaplasia. When endoscopically evident, columnar metaplasia with goblet cells in the esophagus is termed BE.

BE is the strongest risk factor for EAC. BE is associated with a risk of EAC that is 40-120 times that of the general population.^{8,9} Furthermore, BE is an extremely common condition, present in approximately 10% of patients with chronic GERD¹⁰ and in 1-2% of the general population.¹¹ Since 10-20% of adult Americans have at least weekly symptoms of GERD,^{12,13} the number of cases of BE in the U.S. is thought to be >2 million. BE does not generally spontaneously regress; barring an intervention, the patient will have BE for life. Most patients harboring BE will not progress to EAC. However, in a proportion (0.2-0.5%/year,)¹⁴ the metaplastic tissue will progress from LGD to HGD, culminating in EAC.^{15,16} Given the poor prognosis of cancer diagnosed symptomatically,^{17,18} current effort is directed toward early detection and treatment. Current strategies for prevention of EAC focus on endoscopic screening and surveillance.¹⁹ In the approach most commonly used in the U.S., patients with chronic heartburn are

Medtronic

COVB2710467

```
Version G 01-DEC-2017
```

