8.3. Inclusion Criteria

- 1) Male or female subjects, age 18 and above.
- 2) Able to read, comprehend, and complete the consent form.
- 3) Clinically fit for an endoscopy.
- 4) One of the following options:
 - b) Previous confirmed diagnosis of Barrett's esophagus with intestinal metaplasia, and Prague classification of at least one circumferential centimeter of BE or a total BE segment length of at least 3 centimeters (C1+ or CXM3+) (BE arm). OR
 - c) If the subject does not have documented Prague Classification prior to screening, but the PI is convinced that the subject will meet the inclusion criteria based on previous documentation (for instance, mention of "long-segment BE," they may enroll the subject in the study at their discretion. The study upper endoscopy must confirm that the subject has C1+ or CXM3+ (BE arm). If (C1+ or CXM3+) is not observed at the time of study endoscopy, the subject may still be enrolled but not included in the data analysis with the BE cohort. The data may be analyzed in a separate cohort. OR
 - d) Self-reported heartburn or regurgitation on at least a monthly basis for at least 6 months (GERD arm).

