Subjects' preferences for Cytosponge versus endoscopic surveillance, as well as willingness to undergo the procedure again, will be measured as proportions, with bivariate and multivariate analyses for predictors of preference performed.

For the second primary objective, to assess the adequacy of samples, sample adequacy will be treated as a dichotomous variable. For purposes of this investigation, an adequate sample will be one in which at least one columnar cell is present. Sample adequacy will be presented as a proportion of subjects who fulfill this definition after up to two total administrations of the Cytosponge, as noted in the methods.

For the first three secondary objectives, to assess the operating characteristics of Cytosponge against various gold standards, initially 2x2 tables will be constructed demonstrating Cytosponge and the gold

COVB2710467

Version G 01-DEC-2017

Page 35 of 61

standard findings (Y/N for BE via endoscopy and Y/N for Intestinal Metaplasia (IM) via biopsies). Both endoscopic evidence of BE and pathological confirmation of specialized IM (intestinal metaplasia with goblet cells) will be used in the final diagnosis of BE. Sensitivity, specificity, positive predictive value, negative predictive value and accuracy will be calculated. Because Cytosponge positivity may vary based on the burden of BE, we will perform sensitivity analyses, defining "positive" cases as those with BE of ≥2 cm in length, and then ≥3 cm in length, to assess impact of disease burden on operating characteristics. Multivariate models controlling for age, sex, burden of disease, and other potential confounders will be constructed, to assess the impact of these factors on test accuracy. Although we do not expect to see an association between the degree of dysplasia and Cytosponge positivity, exploratory analyses will be performed using degree of dysplasia as a predictor variable, and Cytosponge positivity as the outcome variable. For the fourth secondary objective, to assess the degree of mucosal abrasion following Cytosponge, endoscopic abrasion scores will be correlated with the presence of columnar cells on the H&E slide made from the Cytosponge samples.

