While the operating characteristics of Cytosponge in our patient population are unknown, the numbers for this post-market study were selected for several reasons. Approximately 50% of the patient population at the involved tertiary care centers have dysplastic BE (25% low-grade dysplasia, 25% high-grade dysplasia), so assessment of 275 patients (with an enrollment ratio of at least \geq 50% BE and \geq 25% GERD) should allow an adequate number of subjects with dysplastic disease to assess performance characteristics with reasonable accuracy. Ten percent of patients with chronic GERD symptoms can be expected to harbor BE, leaving us 75 patients with which to assess specificity, as well as to assess acceptability in patients without disease. For the safety perspective, a sample size of 50 will have greater than 90% probability of detecting a rare event that occurs at a rate of 5%. Results of this study will be used to provide more accurate parameters for power of subsequent studies.

All individuals offered the Cytosponge will be included in analyses of acceptability and adequacy of sampling. All individuals with adequate Cytosponge samples and endoscopy (within 48 hours of Cytosponge) will be included to determine the sensitivity for diagnosis of BE from the TFF3 data (95% confidence intervals will be used).

In an effort to understand the sensitivity and specificity of the test, an interim analysis of the data, based on the statistical methodology outlined above, may be performed after approximately half the study subjects have primary outcomes.

To assess safety (fifth secondary objective), the number and percentage of subjects with adverse events related to Cytosponge administration will be summarized by MedDRA system organ class and preferred term overall, and by severity.

COVB2710467

Version G 01-DEC-2017

Page 36 of 61

14. Ethics

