Revision 2.0

up to 2 total administrations of the Cytosponge, as noted in the methods.

Page 9 of 13

For the first three secondary objectives, to assess the operating characteristics of Cytosponge against various gold standards, initially 2x2 tables will be constructed demonstrating Cytosponge and the gold standard findings (Y/N for BE). Both endoscopic evidence of BE of C1 or CXM3 or greater length and pathological confirmation of specialized IM (intestinal metaplasia with goblet cells) will be used in the final diagnosis of BE. Sensitivity, specificity, positive predictive value, negative predictive value and accuracy will be calculated. Because Cytosponge positivity may vary based on the burden of BE, we will perform sensitivity analyses, defining "positive" cases as those with BE of ≥2 cm in length, and then ≥3 cm in length, to assess impact of disease burden on operating characteristics. Multivariate models controlling for age, sex, burden of disease, and other potential confounders will be constructed, to assess the impact of these factors on test accuracy. Although we do not expect to see an association between the degree of dysplasia and Cytosponge positivity, exploratory analyses will be performed using degree of dysplasia as a predictor variable, and Cytosponge positivity as the outcome variable. For the fourth secondary objective, to assess the degree of mucosal abrasion following Cytosponge, endoscopic abrasion scores will be correlated with the presence of columnar cells on the H&E slide made from the Cytosponge samples.

To assess safety (fifth secondary objective), the number and percentage of subjects with adverse events related to Cytosponge administration will be summarized by MedDRA system organ class and preferred term overall, and by severity.

5 Determination of Sample Size

This study will enroll up to 275 subjects with an enrollment ratio of at least \geq 50% BE and \geq 25% GERD. While the operating characteristics of Cytosponge in our patient population are unknown, the numbers for this post-market study were selected for several reasons:

Revision 2.0

Page 10 of 13

- Approximately 50% of the patient population at the involved tertiary care centers have dysplastic BE (25% low-grade dysplasia, 25% high-grade dysplasia), so assessment of 275 patients should allow an adequate number of subjects with dysplastic disease to assess performance characteristics with reasonable accuracy.

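### As written, the objective 1 accuracy table counts a previously proven Barrett's subject as a non-case when study biopsies miss intestinal metaplasia, which biases specificity down

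*SAP*

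**What the plan says.** SAP 6.6.1.1.3 sets the reference for secondary objective 1: the assay is judged "against a gold standard of upper endoscopy with biopsies for endoscopic surveillance in subjects with BE who demonstrate an adequate sample". For objectives 1 to 3 together, the SAP then says "two-by-two tables will be constructed demonstrating Cytosponge and the gold standard findings (Y/N for BE", and derives sensitivity, specificity, predictive values and accuracy from those tables. It expects sensitivity and specificity each above 90%.

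The case definition is in the Statistics row of SAP section 4, and in the Protocol synopsis: "Both endoscopic evidence of BE of C1 or CXM3 or greater length and pathological confirmation of specialized IM" go into the final diagnosis. Protocol section 13 also requires "endoscopic evidence of BE and pathological confirmation of specialized IM", but without the length threshold.

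The main route into the BE arm (Protocol 8.3) requires "Previous confirmed diagnosis of Barrett's esophagus with intestinal metaplasia". Exclusion criterion 7 removes anyone with earlier ablation or resection. Protocol 4.2 says that "BE does not generally spontaneously regress; barring an intervention, the patient will have BE for life", and Protocol 4.1 lists biopsy sampling error among the weaknesses of endoscopy.

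On the analysis set, Protocol section 13 says "All individuals with adequate Cytosponge samples and endoscopy (within 48 hours of Cytosponge) will be included to determine the sensitivity". That sentence does not name specificity.

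**The concern.** A Y/N table has no third cell. Take a BE-arm subject with documented prior IM who is biopsied at the study endoscopy and in whom no goblet cells are found. That subject fails the both-required rule and becomes reference-negative. Under the SAP and synopsis wording, so does a subject with a documented Prague class whose study endoscopy falls under C1/CXM3. On the Protocol's own account, many of these subjects probably still have BE. A TFF3-positive result in them moves from true positive to false positive, and a TFF3-negative result from false negative to true negative. Specificity, positive predictive value and accuracy go down, and negative predictive value goes up.

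Specificity would then partly measure how often biopsies miss IM in known BE, rather than how the test behaves in people without BE. SAP 6.5 gives understanding of sensitivity and specificity as the reason for the optional interim analysis. Protocol section 13 intends the results to inform the power of later studies. A distorted figure would carry into both.

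**Working it through.** **The plan's own count of non-BE subjects.** Protocol section 13 expects 10% of GERD patients to have BE and gives 75 patients for specificity. The 25% GERD floor gives 275 × 0.25 × 0.90 = 61.9, about 62, so 75 does not follow from the floor. It needs 75 / 0.90 = 83.3 GERD subjects, or 30% of 275, which the enrollment rule allows. I therefore use the two ends of the range, with two arms adding to 275:

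- 50% BE: 137.5, about 138 BE; non-BE GERD 137.5 × 0.90 = 123.75, about 124.
- 75% BE: 206.25, about 206 BE; non-BE GERD about 62.

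**Other inputs.** Protocol 6.2 reports sensitivity 90% and specificity 94% in the UK study of 504 GERD subjects, and 84% and 92% in the follow-up series of 334. The share *f* of BE-arm subjects not re-confirmed is my assumption: 2%, 5% or 10%.

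**Formula.** With N0 true non-BE subjects and m = f × (BE-arm n) unconfirmed subjects taken to be true BE:

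apparent specificity = [N0 × sp + m × (1 − se)] / (N0 + m)

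Example for 206 BE, 62 non-BE, f = 5%, se 0.84, sp 0.92: m = 10.3; (57.04 + 1.648) / 72.3 = 0.812.

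| BE / non-BE | se, sp | f = 2% | f = 5% | f = 10% |
|---|---|---|---|---|
| 138 / 124 | 0.84, 0.92 | 0.903 | 0.880 | 0.844 |
| 138 / 124 | 0.90, 0.94 | 0.922 | 0.896 | 0.856 |
| 206 / 62 | 0.84, 0.92 | 0.873 | 0.812 | 0.730 |
| 206 / 62 | 0.90, 0.94 | 0.888 | 0.820 | 0.731 |

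The loss against the true value is about 2 to 5 points at 2%, 4 to 12 at 5%, and 8 to 21 at 10%.

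**How few subjects matter.** The m that brings expected specificity down to 0.90 is N0 × (sp − 0.90) / (0.90 − (1 − se)):

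- 62 non-BE: 62 × 0.02 / 0.74 = 1.7, or 62 × 0.04 / 0.80 = 3.1. Two to four subjects are enough to fall below.
- 124 non-BE: 124 × 0.02 / 0.74 = 3.4, or 124 × 0.04 / 0.80 = 6.2. Four to seven are enough.

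**A limit of the model.** It gives unconfirmed subjects the same TFF3-positive rate as other BE subjects. If they carry less IM, that rate may be lower and the bias smaller. The bias vanishes only if their rate falls to the false-positive rate of 6-8% (1 − 0.94 and 1 − 0.92).

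**The case against.** **The outcome is inferred, not stated.** No sentence says that a proven BE subject becomes a non-case. Protocol section 13 mentions Y/N for BE by endoscopy and Y/N for IM by biopsy, which can be read as recording the components separately. That is fair, but the same section then requires both for the final diagnosis.

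**Some subjects are handled.** A reader might infer that every non-confirmation makes a non-case. The documents do not support that. Under Protocol 8.3, a subject enrolled without a documented Prague class who does not show C1+/CXM3+ at the study endoscopy leaves the BE cohort and may be analysed separately. The rule does not cover missed IM, or subjects with a documented Prague class. The requirement for biopsies within two months beforehand helps only subjects ablated on the same day.

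**Specificity is meant to come from GERD patients.** Protocol section 13 says so, but only in the sample-size rationale. The SAP omits it, and SAP 6.1.3 defaults to all available data on all enrolled subjects.

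**Objective 2 already uses worst-ever histology.** Prior IM then stays a case. This is a real counter-analysis, but a separate one: it leaves the objective 1 table, where the expectation above 90% is stated, unchanged.

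**A stronger reading does not hold.** From "in subjects with BE who demonstrate an adequate sample on Cytosponge assessment" a reader might infer that the objective 1 table is confined to BE subjects, so that specificity collapses to one minus sensitivity. That conflicts with the Protocol's plan to use GERD patients and with the SAP's own expected specificity.

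**A TFF3-positive result in an unconfirmed subject is not proven correct.** The non-regression statement is qualified, Protocol 4.1 also cites inter-observer variability in histology, and the sampling-error remark under objective 2 concerns dysplasia. This stands, and is a reason to show these subjects openly rather than simply reclassify them.

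**Conclusion.** The concern holds in limited form. Followed as written, the both-required definition and the Y/N table count a biopsied BE-arm subject with prior IM but no IM on study biopsy as reference-negative, and no rule prevents it. The same applies to a documented-Prague subject measured under C1/CXM3, but only under the SAP and synopsis definition; Protocol section 13 has no length threshold, and the wordings need reconciling.

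Apparent specificity would be about 87-92%, 81-90% and 73-86% at 2%, 5% and 10% non-confirmation, against a true 92-94%. These are scenarios: they rest on an assumed rate, on the unconfirmed subjects being true BE, and on the prior accuracy figures carrying over. At 2% and with the larger GERD arm, 90% can still be met. Severity is should-fix: the objective is secondary, the study is a pilot, and the figure above 90% is an expectation with no test or decision rule.

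**What to change.** In SAP 6.6.1.1.3 and Protocol section 13, before accuracy results are seen:

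1. State who forms each row of the objective 1 table, using one case definition in both documents.
2. Report specificity in GERD-arm subjects with no prior or current BE.
3. Show BE-arm subjects with prior IM who are not re-confirmed in a separate row, by TFF3 result.
4. Report sensitivity, specificity, both predictive values and accuracy three ways: with these subjects excluded, classed as BE, and classed as non-BE (as now written).
5. Apply the same rule to proven BE shorter than the cut-off in the ≥2 cm and ≥3 cm analyses, where the plan does not say whether such subjects become non-cases or drop out.

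The cost is wording and some extra table rows, with no new data. The specificity denominator shrinks: at 5% non-confirmation, from 72.3 to 62 or from 130.9 to 124. At equal proportions the interval widens by about 8% (√(72.3/62) = 1.08) or 3% (√(130.9/124) = 1.03). Excluding discordant subjects can also flatter accuracy, which is why all three versions should appear.
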